7.2. Simon's two stage design

We will follow stopping rule in Simon's two-stage design if high incidence of new SAEs occurred in study participants. In the first stage, a subset of 5 patients will be enrolled. If all the 5 patients develop new SAE in the study period, we will declare the study is not safe for patients and will stop the trial immediately to check if FMT is related to these SAEs. If less than 5 patients develop SAEs in the first stage, we will proceed to second stage to enroll another 5 patients. If 7 out of the total 10 patients enrolled develop at least one SAE, we will stop again and check if FMT is related to these SAEs. Otherwise the enrollment will be continued until the sample size for the primary outcome analysis is met.

Assuming the probability of the new SAE is 76% among study participants, following the 5/5 and 7/10 two-stage stopping rule, we will have 25% chance to stop in the first stage, and 80% chance to stop in the second stage. If probability of new SAE increases to 0.96, we will have 82% chance to stop in the first stage, and 100% chance to stop in the second stage.

True probability of SAE	0.76	0.80	0.90	0.96	0.98
Probability to stop in the first stage	0.25	0.33	0.59	0.82	0.90
Probability to stop in the second stage	0.80	0.88	0.99	1.00	1.00

Table. The probability of stop following 5/5 and 7/10 stopping rule in two-stage design.

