3.2.1. Inclusion Criteria

Male and female children and young adults, aged 5 years to 30 years, who meet the following inclusion criteria, will be enrolled in the study.

An initial subset of 10 subjects will be limited to patients with mild to moderate ulcerative colitis (i.e., PUCAI < 65) and to individuals ≥ 12 years of age. If FMT appears to be safe in this subset of patients after 8 weeks in the study (to be assessed by a Data Safety Monitoring Board), expanded enrollment as is described above will occur.

All patients must satisfy below criteria:

- 1. Have UC (PUCAI >9) and have failed, are intolerant to, or have refused first-line maintenance therapy.
- 2. Have had visual or histologic evidence of inflammation confirmed through colonoscopy ideally within 90 days but no more than 105 days prior to randomization.
- 3. Have negative test results for Hepatitis B (HBV), Hepatitis C (HCV), and Human Immunodeficiency Virus (HIV).
- 4. Have a negative urine hCG test if female of childbearing potential.
- 5. Able to swallow antibiotic, FMT or placebo capsules.
- 6. Able to give informed consent and/or assent as appropriate (patients 12-17 will be asked to provide written assent, patients 5-11 will be observed for assent or dissent behaviorally, or with verbal/written communication)
- 7. Willing and able to participate in the study requirements, including serial stool collection, survey completion and clinic visits.
- 8. Willing to undergo telephone follow-up to assess for safety and adverse events.
- 9. Must be free of any known food allergy.
- 10. Agrees and willing to have an enema for purposes of induction therapy.

Patients who have disease that has required other medications (including steroids, immunosuppressives, and biologics) will be included.

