4.1.4. Blinding and Randomization

The first ten eligible subjects will be randomized in a 1:1 ratio according to a pre-determined block randomization procedure to receive either FMT or placebo. If safety allows, the remaining cohort of 50 eligible subjects will be randomized in a 1:1 ratio according to a pre-determined block randomization procedure to receive either FMT or placebo. An unblinded pharmacist or delegate will maintain the randomization list ensuring subjects are randomized appropriately and dispensed the correct treatment. The investigator, research personnel and study subjects will be blinded to treatment assignments.

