6. SAFETY ASSESSMENT

6.1. Adverse Event Assessment and Reporting

Comprehensive assessments of any apparent adverse event(s) (AE) experienced by the study subject will be performed throughout the course of the study.

The PI will submit reports of unexpected Serious adverse events (SAEs) and other unanticipated problems to the Institutional Review Board (IRB) at Boston Children's Hospital and to OpenBiome according to their policies.

The PI will report events that are both serious and unexpected and that are associated with FMT/study intervention to the FDA and other applicable health authorities within the required timelines as specified in 21 CFR 312.32 (IND Safety Reports).

The following unexpected AEs will be assessed, recorded and reported to the Data Safety Monitoring Board (DSMB) on an expedited basis: all SAEs, AEs grade 3 (according to CTCAE 5.0 (31) if applicable) or above, and any unexpected AEs grade 2 or above that is possibly or probably related to FMT (as determined by a blinded investigator). Only an AE that meets the above criteria will be recorded and reported. Each reported AE will be described by its duration (i.e., start and end dates), regulatory seriousness criteria if applicable, expectedness, suspected relationship to the study treatment, and actions taken (a blinded investigator will determine expectedness, severity and relationship to study treatment).

Individual subject participation will be temporarily halted until the DSMB determines appropriateness of re-initiation of therapy in any subject experiencing an adverse event resulting in: an Emergency Department visit that is possibly or probably related to FMT, significant worsening of their disease, or experiences 1 SAE Grade \geq 3.

Individual subject participation in the study will be permanently stopped if a SAE Grade ≥ 3 is deemed possibly or probably related to FMT, including any hospital admission.

If 2 or more subjects experience 1 SAE grade \geq 4, all study activities will be halted until the DSMB determines appropriateness of re-initiation of therapy in any subject.

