7. STATISTICAL CONSIDERATIONS

7.1. Power Calculation

The primary aim of this phase I/II study is to establish whether or not FMT is a safe treatment for children and young adults with UC. Based on clinical experience, adverse events (AEs) in IBD patients are common and include abdominal pain, cramping, diarrhea, fever, bloody stool, vomiting, frequent defecation, joint pain, and eye pain. It's estimated that 70% of patients in any given year will experience a flare of their disease and have some or a combination of these symptoms. Safety, therefore, needs to be assessed relative to the high prevalence of AEs in this population. For the primary outcome, we will take any new reported SAEs or worsening of the existing AEs during the study period following enrollment into account.

The study will be powered for equivalence in the proportion of new SAEs or worsening of the existing AEs, assuming null (Ho) and alternative (Ha) hypotheses defined as follows:

$$\begin{split} & \text{Ho: } p1-p2 \leq \text{-}\delta_L \ \text{ or } p1-p2 \geq \delta_U. \\ & \text{Ha: } \delta_L \leq p1-p2 \leq \delta_U \end{split}$$

where p1 is the proportion of new SAEs or worsening of the existing AEs in the placebo group, p2 is the proportion in the FMT group, δ_L is the lower margin and δ_U is the upper margin. We expect to enroll a total of 60 patients into this study for a total of 30 FMT and 30 placebo patients. Assuming the rate of new incident SAEs or worsening of existing AEs in the placebo group is 10%, there will be 82% power to reject Ho that the difference in proportions is 0.20 or greater from zero in the same direction. Similarly, we will have an 85% power to reject a difference of 0.25 or greater if the rate of new incident SAEs or worsening of existing AEs increases to 15%.

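### The section 7.2 stopping rule pools SAEs over both randomised arms, so it would seldom stop the trial for harm confined to FMT

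*Combined protocol and SAP*

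**What the plan says.** Section 7.2 sets a two-stage rule, to be used "if high incidence of new SAEs occurred in study participants". Stage one stops if five of the first five patients have a new SAE. Stage two reads: "If 7 out of the total 10 patients enrolled develop at least one SAE, we will stop again and check if FMT is related". Neither count is split by arm, and relatedness to FMT is examined only once the pooled count has been reached. The operating characteristics start from a single rate for everyone, "Assuming the probability of the new SAE is 76% among study participants", and the table runs from 0.76 to 0.98.

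Section 4.1.4 states: "The first ten eligible subjects will be randomized in a 1:1 ratio". Section 7.1 plans on a placebo rate of 10%, with 15% as the alternative, for a composite of new SAEs and aggravated existing AEs.

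Two other controls matter here. Section 6.1 has a study-wide halt, "If 2 or more subjects experience 1 SAE grade" 4 or higher, as well as halts for individual subjects. Section 3.2.1 makes wider enrolment depend on a DSMB assessment of the first ten: "If FMT appears to be safe in this subset of patients after 8 weeks in the study".

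**The concern.** The rule is there to stop the trial early if FMT proves harmful. A pooled count with one common rate describes a single-arm cohort, whereas the first ten patients are a randomised mix of FMT and placebo. If the harm comes from FMT, only about half the patients can show it, and the threshold of seven exceeds the number of FMT patients.

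Safety is the trial's primary aim. Passing this point opens enrolment to children from age 5 and to disease beyond mild to moderate. An IRB or DSMB member reading the table would expect at least an 80% chance of stopping at an SAE rate of 76%. The question is how much of that remains under 1:1 allocation.

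**Working it through.** **Inputs.** The rule is 5/5, then 7 or more of 10 (section 7.2). Allocation is 1:1 in blocks (section 4.1.4), taken as 5 FMT and 5 placebo; block size is not stated. Placebo rates are 10% and 15% (section 7.1). FMT rates of 76%, 90% and 100% are scenarios; the first two are also columns of the plan's table.

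**The plan's own table.** With one common rate p, stage one is p^5 and stage two is P(X ≥ 7), X ~ Bin(10, p).

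| p | 0.76 | 0.80 | 0.90 | 0.96 | 0.98 |
|---|---|---|---|---|---|
| p^5 | 0.254 | 0.328 | 0.590 | 0.815 | 0.904 |
| P(X ≥ 7) | 0.799 | 0.879 | 0.987 | 1.000 | 1.000 |

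Both rows round to the printed values, so the table is correct for a common rate.

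**Highest pooled rate under 1:1 allocation.** If every FMT patient has an SAE, the average rate is (1.00 + 0.10)/2 = 0.55 or (1.00 + 0.15)/2 = 0.575. Both lie below the table's lowest column.

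**All five FMT patients have an SAE.** Reaching seven then needs at least 2 of 5 placebo SAEs, with probability 1 − (1 − q)^5 − 5q(1 − q)^4:

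- q = 0.10: 1 − 0.5905 − 0.3281 = 0.081
- q = 0.15: 1 − 0.4437 − 0.3915 = 0.165

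The first look adds little. It matters only if four or five of the first five patients are on FMT. In a single random block of ten, those splits have probability 25/252 and 1/252, and the rule then stops with probability 0.147 and 1.000 at q = 0.10. Overall: (226 × 0.0815 + 25 × 0.1471 + 1)/252 = 0.092. At q = 0.15 the same calculation gives (226 × 0.1648 + 25 × 0.2431 + 1)/252 = 0.176.

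**Probability that either look stops the trial.** These come from exact enumeration with binomial SAEs in each arm. The lower figure has 2 or 3 FMT patients in the first five, equally likely; the upper has a random split.

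| FMT SAE rate | Placebo 10% | Placebo 15% |
|---|---|---|
| 76% | 2.5–2.8% | 5.4–5.8% |
| 90% | 5.2–5.8% | 10.7–11.4% |
| 100% | 8.1–9.2% | 16.5–17.6% |

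**What would restore 80%.** With every FMT patient having an SAE, the placebo SAE rate would have to be about 49%.

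**Threshold without the arm problem.** If all ten share one rate, the rule stops 18% of the time at 50% and 1.2% at 30%. The thresholds are therefore high in any case, and pooling makes this worse.

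**Section 6.1 study-wide halt.** Suppose all five FMT patients have an SAE and a share s is grade 4 or higher (s is assumed; the documents give none). P(at least 2 of 5) is 0.263, 0.472 and 0.813 for s = 0.2, 0.3 and 0.5. Any placebo events of that grade would add to this.

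**The case against.** The strongest reply is that section 7.2 does not stand alone. Under section 6.1, unexpected SAEs go to the DSMB on an expedited basis. A subject with a grade 3 or higher SAE is paused, and permanently stopped if it is possibly or probably related to FMT. Two subjects with grade 4 or higher SAEs halt the study. Under section 3.2.1, enrolment widens only if the DSMB finds the first ten reassuring. Missing 7/10 therefore does not by itself let the trial proceed. This stands, and it limits the consequence. However, five FMT patients with grade 3 SAEs would not trigger the study-wide halt, the relatedness call is made by a blinded investigator, and the DSMB review has no stated criterion or commitment to data by arm.

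A second reply is that the 10–15% is borrowed from a composite endpoint, and that section 7.2 may use the term SAE loosely for common flare symptoms, given the 70% yearly flare figure in section 7.1. The result does depend on the placebo rate: at 50% placebo and 100% FMT the rule would stop about 81–82% of the time. But read strictly, SAEs alone cannot be more frequent than the composite. At an assumed 5% placebo rate, stopping falls to 2.3–3.1% even with every FMT patient affected. A 70% yearly rate, if constant, is about 17% over eight weeks: 1 − 0.30^(8/52) = 0.17.

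Third, pooling allows monitoring without unblinding. That is a fair reason for a pooled count seen by investigators, but the DSMB in section 6.2 is independent of the principal investigator and includes a biostatistician, so it can hold counts by arm.

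**Conclusion.** The concern holds. The table is computed correctly, but for a cohort with one common SAE rate, not for the randomised ten. At the placebo rates of section 7.1, the rule stops about 8–18% of the time even when every FMT patient has an SAE, and less than 6% of the time at a 76% FMT rate. The table also shows no arm-specific scenario and none near the planning rates.

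The figures assume an exact 5:5 split, inferred from the separate block randomisation of the first ten, and a placebo SAE rate equal to the composite rate, which favours the rule. If patients were instead randomised without blocks, contrary to section 4.1.4, stopping with every FMT patient affected would be about 27% and 33%, still far from the printed 80–100%. Because other safeguards exist, the defect is a weak stopping rule and a misleading table, not an absence of protection.

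**What to change.** In section 7.2:

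1. State that the boundary applies to SAEs among FMT recipients, and that the DSMB receives counts by arm.
2. Have the DSMB biostatistician reset the thresholds for about five FMT patients.
3. Replace the table with stopping probabilities under 1:1 allocation, over a range of FMT and placebo SAE rates that includes 10–15%.
4. State that the section 6.1 halt runs in parallel and that whichever is reached first governs.

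For illustration only, with a single look at five FMT patients:

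| FMT SAE rate | 10% | 15% | 50% | 76% |
|---|---|---|---|---|
| Stop at 3 of 5 | 0.9% | 2.7% | 50% | 91% |
| Stop at 2 of 5 | 8.1% | 16.5% | 81% | 98.7% |

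The lower threshold is more sensitive but would stop about one trial in six at a 15% rate. That choice belongs to the DSMB, as does any additional earlier look.

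The cost is a rewrite of one section and a short recalculation. The DSMB sees unblinded counts while the investigators remain blinded. No further patients are needed and the primary analysis is unchanged.

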7.3. Data Analysis

All patients who are eligible, randomized, and have received at least one-dose of the study medication including antibiotics/placebo in the first week will be included into the analysis for primary outcomes to assess the safety and tolerability of FMT, as this will be a per protocol (and not intent-to-treat) analysis . Continuous variables will be presented as mean and standard deviation (SD) or median and interquartile range (IQR), depending on the distribution of the data. Categorical variables will be presented as number and percentage. Disease severity (PUCAI) and patient characteristics at baseline will be compared between the treatment groups to determine whether or not randomization resulted in balanced groups. Methods of 2-group comparison will include Student's t-test, the Mann-Whitney test, Pearson chi-square test, and Fisher exact test, depending on the distribution of the variable under consideration. The primary outcome of safety will be assessed via a 2×2 cross-tabulation, where the proportion of patients with new incident SAEs or upgrade of existing AEs in the FMT group will be compared to the proportion in the placebo group. Two one-sided tests for equivalence (32) will be constructed and the overall *P* value taken to be the larger of the lower and upper tests. Statistical significance will be assessed at *P*<0.05.

For the second outcome, we will use longitudinal data analysis methods to investigate changes in inflammatory biomarkers including stool calprotectin, stool lactoferrin, serum ESR/CRP, albumin, and hematocrit over the study period. Generalized Estimating Equations will be performed to examine the association between FMT and changes in these biomarkers.

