3.2.3. Subject withdrawal criteria

All subjects are free to withdraw from participation in the study at any time, for any reason, specified or unspecified. A subject may be withdrawn from the study under any of the following circumstances:

- Withdrawal of informed consent or assent when applicable.
- If, in the opinion of the investigator, IRB or DSMB, it is no longer in the subject's best interest to continue in the study.
- The subject no longer meets the inclusion criteria or meets any of the exclusion criteria.
- Lack of compliance with study procedures or study treatment, as determined by the investigator.

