3.2.4 Screen failure

A subject who consented to participate in the study but who was disqualified during screening procedures and *never began Antibiotic/Placebo conditioning* will enter Passive follow-up, which means the subject may reach out to the study team for a second opinion for follow-up care or any other medically related reason. These subjects will not be included in the per protocol analysis.

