5.2. Study treatment and procedures

5.2.1. Screening and Enrollment

Patients with active UC that are part of the Boston Children's Hospital Gastroenterology and Nutrition clinic as well as referrals from outside of BCH will be pre-screened for study participation. Potential subjects who agree to participate in the study will have a medical exam with labs to assess eligibility. Participants will also undergo a baseline serologic assessment of HIV, HBV and HCV status within 2 weeks prior to the first FMT dose. Females who have achieved menses will undergo urine hCG testing. These four lab tests are considered for research purposes only.

It is expected that study participants will receive ongoing clinical care at BCH for the duration of the study. Study participants, who self-refer or are referred by a GI provider not at BCH, will have their primary GI provider notified of their participation in the FMT study and follow up clinical care at BCH during the course of the study at planned intervals. The study PI will provide the primary GI provider with contact information to relay any questions and concerns during the study period. At the completion of the subject's involvement in the study, the PI will provide a final written and/or verbal report to the primary GI provider for continuity of care.

Presence of active mucosal inflammatory bowel disease (active colitis) is an eligibility requirement for this study. Subjects with evidence of inflammation in a prior staging colonoscopy completed no more than 105 days will not be required to repeat a standard staging colonoscopy solely for the purposes of research. Subjects who have no evidence of active disease by endoscopic scoring of disease at the time of staging colonoscopy will not be randomized and will be excluded from the study.

An initial subset of 10 subjects will be limited to patients with mild to moderate Ulcerative colitis (i.e., PUCAI < 65) and to individuals ≥ 12 years of age.

Upon confirmation of eligibility and completion of randomization, subjects will receive an induction antibiotic regimen (or corresponding placebo if in placebo arm) for one week to decrease levels of indigenous microflora (Study Day -8 until Day -1).

The antibiotic regimen will include:

1) A double antibiotic capsule containing vancomycin 125 mg and polymixin 62.5 mg to be administered orally (PO) according to the following body surface area (BSA) parameters:

BSA* (m ²)	Capsule	Frequency				
< 0.5	1	3 times a day				

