5.2.5. End of Study or Early Termination Visit

If withdrawing early from the study for any reason, subjects will be invited to come in for a final visit to provide a stool sample and routine labs (if indicated).

Follow-up for subjects who signed the consent form, but did not complete the study (**does not include screen failures**) is as followed:

- Active (full follow-up schedule) if subject received at least one dose of FMP IP.
- Active-abbreviated (Subjects will be called weekly for one month and then once at the second month for a total of two months), for subjects that received at least one dose of antibiotics and/or placebo IP but did not complete blinded treatment period or receive any FMP.

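### Section 7.3 restricts the primary safety set to *eligible* treated subjects and calls it per protocol, without saying when eligibility is judged; as worded, a dosed subject could be left out of the safety test

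*Combined protocol and SAP*

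**What the plan says.** Section 7.3 sets three conditions for the primary analysis: "All patients who are eligible, randomized, and have received at least one-dose of the study medication including antibiotics/placebo in the first week". These subjects "will be included into the analysis for primary outcomes to assess the safety and tolerability of FMT", and the reason given is "as this will be a per protocol (and not intent-to-treat) analysis". No all-treated safety set is defined elsewhere, and the set carries no rule on adherence, minimum FMT exposure or major deviations.

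Four other places bear on what *eligible* means and who is counted:

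- Section 3.2.4 is the only other mention of the per-protocol analysis. It concerns screen failures who never started conditioning: "These subjects will not be included in the per protocol analysis".
- Section 5.2.1 puts the eligibility check first: "Upon confirmation of eligibility and completion of randomization, subjects will receive an induction antibiotic regimen". Section 3.2.2 likewise applies the exclusion criteria at screening.
- Section 3.2.3 lists two grounds for withdrawal that can arise after dosing: "The subject no longer meets the inclusion criteria or meets any of the exclusion criteria" and "Lack of compliance with study procedures or study treatment, as determined by the investigator". It says nothing about the analysis set.
- Section 5.2.5 provides abbreviated follow-up "for subjects that received at least one dose of antibiotics and/or placebo IP but did not complete blinded treatment period or receive any FMP", so the plan expects some subjects to take a first dose and never receive FMT.

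Section 5.2.3 unblinds each subject after the week 8 dose.

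**The concern.** The primary question is whether FMT is safe, so the primary set should contain everyone who was randomised and took study product. Adding *eligible* to *randomised and dosed* has an effect only if it removes someone, and those it would remove are exposed subjects. Their events would drop out of both numerator and denominator.

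Eligibility findings after dosing are plausible. Earlier donor FMT, recent antibiotics and recent dose changes all rest on history that may be corrected later. Active *C. difficile* is an exclusion, yet the schedule in section 5.1 has no row of its own for that test. The plan does not say who makes a late eligibility call, or by when, and after week 8 the arm is known.

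The label adds to the uncertainty. A reader who sees *per protocol* expects an adherence-based set, but one antibiotic or placebo dose is enough to enter this one.

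**Working it through.** **Inputs.** Section 7.1 gives 30 per arm, a placebo event rate of 10% and a margin of 0.20 (second scenario: 15% and 0.25). Section 7.3 gives two one-sided tests at P<0.05, taken here as 0.05 for each test. The documents do not say how many subjects might be found ineligible, so 0 to 3 is an assumed range. The event counts below are illustrative.

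**The plan's own figures.** With equal true rates p, SE = √(2p(1−p)/30), and power against one margin is Φ(margin/SE − 1.645).

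- p = 0.10, margin 0.20: SE = 0.0775, power 82.6% (stated 82%).
- p = 0.15, margin 0.25: SE = 0.0922, power 85.7% (stated 85%).

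These are powers for one margin only. For both tests together, 2Φ(margin/SE − 1.645) − 1 gives 65.1% and 71.4%. That is a separate matter, but it confirms the inputs. If the filter removed 1, 2 or 3 subjects per arm, the one-margin power in the first scenario would be 81.4%, 80.2% or 79.0%.

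**What one removal can do (margin 0.20).** Let d = FMT rate − placebo rate. The Wald one-sided 95% upper limit is d + 1.645 × SE, with SE = √(p₁(1−p₁)/n₁ + p₂(1−p₂)/n₂). The lower test passes easily in every row, so the upper limit decides.

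| Placebo | FMT | Subject removed | d | SE | Upper limit | Equivalence |
|---|---|---|---|---|---|---|
| 3/30 | 5/30 | none | 0.0667 | 0.0873 | 0.210 | not shown |
| 3/30 | 4/29 | FMT, with event | 0.0379 | 0.0843 | 0.177 | declared |
| 3/30 | 5/29 | FMT, no event | 0.0724 | 0.0890 | 0.219 | not shown |
| 2/29 | 5/30 | placebo, with event | 0.0977 | 0.0827 | 0.234 | not shown |

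The P value is 0.063 in the first row and 0.027 in the second. A score test gives 0.076 and 0.041, so the reversal does not depend on the Wald form. It does depend on the margin: at 0.25, both of these limits fall inside.

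**Long-run behaviour.** True rates are set at 10% and 30%, so the true difference equals the margin and declaring equivalence is an error. The Wald procedure is enumerated exactly over both binomials.

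| FMT subjects removed | Irrespective of outcome | Only subjects with events (assumed worst case) |
|---|---|---|
| 0 | 5.4% | 5.4% |
| 1 | 4.9% | 8.5% |
| 2 | 4.5% | 13.0% |
| 3 | 5.0% | 21.2% |

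The filter itself does not inflate the error rate. Removal that depends on outcome does.

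**The case against.** The strongest reply is that *eligible* simply means confirmed eligible before randomisation. Sections 3.2.2 and 5.2.1 put the check at screening, and 3.2.4 excludes only people who never began conditioning. Read together, the sentence in 7.3 is the mirror image of 3.2.4 and drops no dosed subject. Section 3.2.3 provides for withdrawal from the study, not deletion from the analysis, and no section describes an eligibility review after dosing. This reading is reasonable, and it rules out saying that treated subjects *will* lose their events. But 7.3 does not adopt it, and if it is what is meant, the word does no work and can go.

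The reply is also right on direction. A reader might infer that the filter favours equivalence. The documents do not support that: it applies to both arms, and two of the three single removals above move the limit away from equivalence. Bias towards equivalence needs selection on outcome. Investigators are blinded during the 8 weeks (section 4.1.4), so the opening lies after the section 5.2.3 unblinding. It is possible but not shown.

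A reader might also infer that counting FMT-arm subjects who took only antibiotics dilutes the comparison and makes the current set wrong. That does not follow. A safety set of all dosed subjects by assigned arm keeps the same people. Their number and event rate are not in the documents, and antibiotics are themselves part of the active regimen. Their inclusion shows that the label is wrong, not that they should be left out.

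Finally, the events are not lost to the trial. Section 5.2.5 keeps full follow-up after one FMT dose, and section 6.1 sends qualifying events to the DSMB.

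**Conclusion.** The point holds as an ambiguity with a real consequence, not as a demonstrated bias. As worded, 7.3 allows a randomised, dosed subject to be left out of the primary safety comparison on an eligibility finding of unstated timing, and it gives the set a name that its definition does not match. Its size cannot be estimated, because the number of late eligibility findings is unknown and may be zero. The exposure is that, with 30 per arm and a margin of 0.20, a single outcome-dependent exclusion can move the upper limit from 0.210 to 0.177 and reverse the conclusion, whereas exclusions unrelated to outcome leave the false-equivalence rate at about 5%. The loss would be confined to the primary test, but that test carries the safety claim. The absence of an adherence-based supportive analysis is not in itself an error in a 60-subject phase I/II plan. This should be fixed, as an improvement that costs nothing under either reading of the text.

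**What to change.** In section 7.3, delete *eligible* and the per-protocol wording. Define the primary safety set as all randomised subjects who took at least one dose of any blinded product (antibiotic, FMT or corresponding placebo), regardless of later eligibility findings, grouped by assigned arm, or by product received if misdispensed. Align the sentence in section 3.2.4 so that it refers to this set.

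Optionally, add a properly defined per-protocol set as a supportive run of the same two one-sided tests: no major eligibility breach, enema received, and a stated minimum number of the 7 weekly capsule doses. Fix the membership rules before any subject's assignment is revealed.

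The cost is a wording change and, if the option is taken, one further run of the same test. No patients, visits or procedures are added, and the power inputs in section 7.1 do not change.
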